1.0 Study Summary

Study Title	Walking to school at Banneker Elementary
Study Design	Phase 1: cross-sectional survey Phase 2: behavioral Intervention
Primary Objective	Phase 1: to identify students and families interested in walking to/from school Phase 2: to provide support to students and families interested in walking to/from school
Secondary Objective(s)	
Research Intervention(s)/ Investigational Agent(s)	Phase 2 involves a behavioral intervention involving health coaching delivered over the phone and through email messaging.
IND/IDE #	N/A
Study Population	Children enrolled at Benjamin Banneker School and their parent(s)
Sample Size	Phase 1: the survey will be sent home with all students enrolled at Banneker; estimated response is 600 parents Phase 2: 30 parent/child dyads
Study Duration for Individual Participants	Phase 1: one survey that takes approximately 10 minutes to complete Phase 2: approximately 6 weeks
Study Specific Abbreviations/ Definitions	

SHORT TITLE:

2.0 Objectives

Phase 1: to identify students and families interested in walking to/from school.

Phase 2: to provide support to students and families interested in walking to/from school, and determine acceptability and appropriateness of the supports.

3.0 Background

Increasing rates of walking to school can lead to improvements in children's overall physical activity and health. Yet, few children walk to school. Walking school bus programs, often included in Safe Routes to School efforts, provide children an opportunity to walk to school in a group accompanied by an adult. This improves safety and support for walking to school. Our community partner, BikeWalkKC, provides walking school bus programming at some local schools in the Kansas City area. However, it is difficult to engage students and families to join these walking school buses and walk to school in general.

The purpose of this study is to test the acceptability and appropriateness of a novel behavioral coaching intervention for increasing the number of students who participate in a walking school bus or walk to school through other means. This study will be conducted at one local school, Banneker Elementary School in KCPS, where BikeWalkKC is providing a walking school bus in the fall of 2019. The walking school bus and BikeWalkKC's involvement is not part of the research study. The research activities, which are being conducted by our team at CMH, involve a cross-sectional survey of all students in the school (Phase 1), and a behavioral coaching intervention to up to 30 students, aimed to transition them from driving to school to walking (either with the walking school bus or through other means).

4.0 Study Endpoints

- 4.1 Completion of Phase 1, then Phase 2 if selected.
- 4.2 No primary safety Endpoint.

5.0 Study Intervention/Investigational Agent

- 5.1 Description: behavioral intervention only. See below:

Intervention

In general, Phase 2 will involve a behavioral coaching intervention. This will include handouts, text messages via Redcap and Outlook (see [name]'s letter of support and the Texting Protocol in IRB submission), phone/skype calls, and email message communications with families (students and parent(s)) for delivering motivational content. The content will be theoretically based and cover skills building, goal setting, and problem solving.

SHORT TITLE:

6.0 Procedures Involved

6.1

Overview and study design

Phase 1 is a cross-sectional survey.

Phase 2 is a single group intervention design with purposeful selection of participants.

6.2

Study measures

Phase 1. The survey asks about current mode of transportation to school, barriers to walking to school, and interest in walking to school through various means. They survey also asks for the student's name, home address, parent email, and parent phone number. The survey is included in this IRB application. It was designed specifically for this study and some items were adapted from the National Safe Routes to School Center's parent survey.

Phase 2. At the end of the intervention, a survey will be administered to families (student and parent(s)) to assess their acceptability and preferences around the intervention content, and its appropriateness.

6.3 Describe:

- Source surveys, slides with scripts (these will include PowerPoint slides that are turned into videos by doing a voiceover and accessible from a study website), parent handouts, and module protocols will be uploaded to myIRB.
- Materials will be accessible here (www.ciparesearchteam.org/walk-to-school) and the URLs will be sent to participants each week via text/email:
 - Module 1: <https://www.ciparesearchteam.org/mod1>
 - Module 2: <https://www.ciparesearchteam.org/mod2>
 - Module 3-5:
<https://www.ciparesearchteam.org/mod35>
 - Nonwalker Module 3:
<https://www.ciparesearchteam.org/mod3>
 - Nonwalker Module 4:
<https://www.ciparesearchteam.org/mod4>
 - Nonwalker Module 5:
<https://www.ciparesearchteam.org/mod5>

6.4 Data collected during the study includes: Student name, address, and parent phone number and email address. This information will be collected via the Phase 1 School Travel Survey to determine

SHORT TITLE:

eligibility of families for Phase 2 or via response to a recruitment flier (if not already obtained from the screener survey).

6.5 Once Phase 2 is complete, no long term follow-up will be completed.

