6.6 N/A – no biologic or radiation review

7.0 Data and Specimen Banking

7.1 N/A not using biorepository

8.0 Genetic Analysis Information

8.1 N/A no genetic analysis

9.0 Sharing of Results with Subjects

9.1 N/A results will not be shared with participants

10.0 Study Timelines

10.1 *Describe:* For Phase 1, the survey will be administered at the beginning of the school year (approximately during the week of Aug 12, 2019). Within 3-8 weeks of the survey administration, a select group of families will be contacted to offer them the intervention (Phase 2). The intervention (Phase 2) will last approximately 6 weeks.

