15.0 Reimbursement, Payment and Tangible Property provided to subjects

- 15.1 N/A – no reimbursement*
- 15.2 Phase 1: No incentive. Phase 2: \$50 for responding to at least 80% of the daily tracking text messages and another \$50 for completing a close-out interview.*
- 15.3 N/A – no tangible property*

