16.0 Withdrawal of Subjects

- 16.1 Withdrawal of participants is not anticipated for any one reason.*
- 16.2 N/A*

SHORT TITLE:

16.3 When a participant decides to withdraw data obtained up to the time of withdrawal will be kept.

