18.2 N/A

19.0 Investigator Assessment of Risk/Benefits Ratio: (IRB makes the final determination)

Select as applicable:	Pediatric Risk Category:	
X	Category 1	Research not involving greater than minimal risk (45 CFR §46.404 and 21 CFR §50.51)
	Category 2	Research involving greater than minimal risk but presenting the prospect of direct benefit to the individual subjects. (45 CFR §46.405 and 21 CFR §50.52)
	Category 3	Research involving greater than minimal risk and no prospect of direct benefit to individual subjects, but likely to yield generalizable knowledge about the subject's disorder or condition. (45 CFR §46.406 and 21 CFR §50.53)
	Category 4	Research not otherwise approvable which presents an opportunity to understand, prevent, or alleviate a serious problem affecting the health or welfare of children. (45 CFR §46.407 and 21 CFR §50.54)
Select if applicable:	Adult Risk Category:	
X	Not Greater than Minimal Risk	
	Greater than Minimal Risk	

SHORT TITLE:

Data Management and Confidentiality

20.1 The data analyses will be descriptive, to summarize the results of the surveys. Qualitative data will also be collected and summarized as part of Phase 2.

20.2 This is a pilot study and the sample size was selected to provide a sufficient number of dyads who complete the intervention and post intervention survey on acceptability.

20.3 All research staff will obtain the proper research training, authorization of access. Study data will be stored using password protection, encryption, physical controls, and separation of identifiers and data [master list] during storage, use, and transmission.

20.4 This study will not obtain a certificate of confidentiality.

20.5 Describe how data or specimens will be handled study-wide:

- Study data will be stored per the [Record Retention and Management Policy](#) and the [Record Retention Schedule 2015](#) according to guidelines for NIH funded studies.
- The CMH study team will have access to the data.

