25.0 Permission/Assent/Consent Process

25.1 Indicate whether you will you be obtaining permission/assent/consent, and if so describe:

- The study staff requests an alteration of the permission/assent process, more specially to use a verbal permission/assent. They have reviewed the checklist for Waiver of Alteration of Consent process and have concluded that the study meets the criteria for number 1.
 - Since this survey collects minimally identifying information (name, address, phone number, and email) and the intervention is minimal (behavioral coaching) the study team is requesting an “opt out” permission/assent process where the participants indicate they do not wish to participate by not completing the form.
 - The recruitment/enrollment phone call for Phase 2 includes a script that explains that participation is voluntary and that withdraw will not affect their relationship with the school or CMH. The script also covers the details/requirements of the study. This script has been uploaded with this amendment submission.

SHORT TITLE:

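### The only named acceptability measure is a survey at the end of about 6 weeks of coaching, so a dyad that withdraws earlier has no named acceptability data

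*Combined protocol and SAP*

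**What the plan says.** Acceptability and appropriateness are the purpose of the study (3.0 Background) and part of the Phase 2 objective (2.0 Objectives). Section 6.2 (Study measures) gives one instrument for them: "At the end of the intervention, a survey will be administered to families (student and parent(s)) to assess their acceptability and preferences". Section 20.2 places the survey at the same point, saying that "the sample size was selected to provide a sufficient number of dyads who complete the intervention and post intervention survey on acceptability".

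On duration, 10.1 says: "The intervention (Phase 2) will last approximately 6 weeks". On leaving early, the Phase 2 script described in 25.1 tells families that "participation is voluntary and that withdraw will not affect their relationship with the school or CMH". Section 16.3 adds: "When a participant decides to withdraw data obtained up to the time of withdrawal will be kept". Section 16.1 foresees no particular reason for withdrawal and gives no rate.

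Three other Phase 2 data sources are mentioned. Section 15.2 offers one payment "for responding to at least 80% of the daily tracking text messages" and another "for completing a close-out interview". Section 20.1 says: "Qualitative data will also be collected and summarized as part of Phase 2".

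**The concern.** A family that gives up on the coaching part-way may hold a view that bears directly on whether the coaching is acceptable. The plan schedules the acceptability question only at the end and describes no step for asking a family that has already left. Section 16.3 preserves earlier data, but nothing labelled as acceptability has been collected by then.

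At stake is the pilot's own question. If leavers and stayers differ in their views, a summary of end-of-intervention responses does not describe everyone who was offered the coaching. This is a data-collection matter first: an answer that nobody requested cannot be recovered in the analysis, however simple or careful that analysis is.

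**Working it through.** The plan has no figure to reproduce. The number of up to 30 dyads (13.1) is a pilot size with no precision target and no dropout allowance behind it. The check is therefore a reading of every Phase 2 data source, followed by one labelled illustration.

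**Step 1. What is collected, when, and from whom**

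| Source | Section | Timing | Stated content | Said to cover withdrawn dyads? |
|---|---|---|---|---|
| Survey | 6.2, 20.2 | End of intervention | Acceptability, preferences, appropriateness | No |
| Daily texts | 15.2 | During the coaching | Tracking | Kept up to withdrawal (16.3) |
| Close-out interview | 15.2 | At the close, by its name | Not stated | No |
| Qualitative data | 20.1 | Not stated | Not stated | No |

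Only the texts are clearly gathered during the coaching, and they are described as tracking.

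**Step 2. Apply this to a dyad that withdraws before the end**

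Under 16.3 its tracking responses are kept, so it does not contribute nothing. The survey has not yet been given. The interview and the qualitative data might record its view, but no passage says so. What remains is a dyad with no named acceptability data.

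**Step 3. What that could do to a summary (illustration; the withdrawal rates are assumptions)**

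Let N = 30 (the planned maximum), w = the share withdrawn, S = the average score or proportion among stayers, and L = the value that leavers would have given. Assume that all stayers answer and no leaver does.

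All-enrolled value = (1 − w) × S + w × L

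Stayers' value minus all-enrolled value = w × (S − L)

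- w = 0.10: 30 × 0.10 = 3 dyads without a response; gap 0.1 × (S − L)
- w = 0.20: 30 × 0.20 = 6 dyads; gap 0.2 × (S − L)
- w = 0.30: 30 × 0.30 = 9 dyads; gap 0.3 × (S − L)

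For example, with S = 4 and L = 3 at w = 0.10, the all-enrolled value is 0.9 × 4 + 0.1 × 3 = 3.9, so the stayers' figure is 0.1 too high. If S = L the gap is zero. If leavers are the more favourable group, its sign reverses. At w = 0 there is no gap. The identity holds in any study with missing responses. It shows how the gap scales and does not estimate it for this trial.

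**The case against.** The strongest reply is that the point rests on silence. Section 6.2 gives the survey to families and does not limit it to completers, and the end of the intervention could be read as the end for that family. The surveys and module protocols (6.3), the texting protocol (5.1) and the Phase 2 script (25.1) were filed separately, and a procedure for early stoppers could sit there. The close-out interview is not made conditional on finishing the coaching, and it may cover the same ground as the survey. Section 16.1 foresees no particular reason for withdrawal. Section 4.1 makes completion the listed endpoint, so a withdrawn dyad would be visible as a non-completer. Finally, this is a small descriptive pilot with no acceptability threshold, so no stated decision turns on a modest shift in an average.

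Much of this stands, and it limits the point. The documents do not forbid asking leavers, and other sources may reach some of them. It does not remove the point. The visible plan describes no step for asking, 16.1 does not say that nobody will leave, and 16.3 and the script both provide for withdrawal. Counting non-completers under 4.1 shows that they left, but not what they thought of the coaching.

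A reader might infer more than the text supports:

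- That withdrawn dyads are excluded from the analysis. Section 20.2 is a reason for the sample size and defines no analysis set.
- That families who do not take up walking, or who disengage without withdrawing, are lost. The nonwalker modules 3 to 5 (6.3) suggest that non-walkers stay in the programme, and nothing in 6.2 excludes a disengaged family.
- That no later contact is allowed. Section 6.5 rules out only long-term follow-up.

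**Conclusion.** The point holds in a limited form. Acceptability is the pilot's purpose, its only named measure comes at the end, and no visible passage offers that measure to a dyad that withdraws earlier. Followed as written, the plan yields acceptability data mainly from families who stayed.

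It is tempting to go on to say that acceptability will be overstated. The documents do not support that: they give neither a withdrawal rate nor any figure on how leavers' views compare, so direction and size are both unknown. The 3, 6 or 9 dyads shown above rest on assumed rates of 10%, 20% and 30% and on full enrolment of 30. The conclusion also assumes that the separately filed materials hold no rule for early stoppers. This is a point to consider, with medium confidence. It is worth acting on because the remedy is cheap and works only if it is in place before families leave.

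**What to change.** - **6.2 and 16.3:** state that every enrolled dyad, including any that stops or withdraws early, is offered the existing acceptability survey or close-out interview when it stops, on a voluntary basis.
- **Phase 2 script (25.1):** add a matching line, so that families know before agreeing that they may be asked and may decline.
- **20.1:** commit to reporting survey respondents out of all enrolled dyads, and identify early stoppers' responses as such, because those families judged a programme that they received only in part.

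If a filed document already contains such a rule, a cross-reference in 6.2 is enough.

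The cost is an amendment and a few extra contacts. At the assumed 10% to 30% withdrawal from 30 dyads that means 3 to 9 contacts. If the existing $50 close-out payment is extended to them, this comes to 3 × $50 = $150 up to 9 × $50 = $450. Some leavers will decline, so the gap may shrink without closing.

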6.6 N/A – no biologic or radiation review

7.0 Data and Specimen Banking

7.1 N/A not using biorepository

8.0 Genetic Analysis Information

8.1 N/A no genetic analysis

9.0 Sharing of Results with Subjects

9.1 N/A results will not be shared with participants

10.0 Study Timelines

10.1 *Describe:* For Phase 1, the survey will be administered at the beginning of the school year (approximately during the week of Aug 12, 2019). Within 3-8 weeks of the survey administration, a select group of families will be contacted to offer them the intervention (Phase 2). The intervention (Phase 2) will last approximately 6 weeks.

11.0 Inclusion and Exclusion Criteria

11.1 Describe the criteria that define who will be included or excluded in your final study sample.

Inclusion Criteria

- Phase 1: Parents of children enrolled at Benjamin Banneker school
- Phase 2: Parents/child dyads who completed the Phase 1 survey OR respond to recruitment attempts and express interest in walking to school. Included parent/child dyads will be:
 - Those who do not participate in LINC program both before **and** after school 4+ days per week (child);
 - Those who live within the school boundary and south of Meyer Blvd (i.e., close enough to an existing walking school bus route) or are willing to drop off and/or pick up the child at a place along an existing walking school bus route (i.e., remote drop off).

SHORT TITLE:

Exclusion Criteria

- Children not enrolled at Benjamin Banneker school
- Those who participate in LINC program both before **and** after school 4+ days per week (child);
- Those who do not live within the school boundary and south of Meyer Blvd (i.e., close enough to an existing walking school bus route) or are not willing to drop off and/or pick up the child at a place along an existing walking school bus route (i.e., remote drop off).

11.2 We will exclude each of the following special populations: (You may not include members of the following populations as subjects in your research unless you indicate this in your inclusion criteria.)

- Adults unable to consent
- Prisoners
- Wards of the state
- Pregnant women may be included, but only in such capacity as parents of other children enrolled at Benjamin Banneker school

12.0 Vulnerable Populations

12.1 If the research involves individuals who are vulnerable to coercion or undue influence, describe additional safeguards included to protect their rights and welfare.

- HRP-416 Checklist has been reviewed.

13.0 Local Number of Subjects

13.1 Phase 1: anticipated that 600 parents will respond to the survey

Phase 2: up to 30 parent/child dyads

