13.2 N/A

13.3 N/A

14.0 Screening and Recruitment Methods

14.1 Phase 1: The survey will be sent home with all students. Banneker staff will give the survey to each student to take home.

Phase 2: We will purposefully select survey respondents based on their survey responses to reach out to via various means to offer the intervention (Phase 2). If the desired enrollment numbers are not reached using this approach, recruitment fliers will be send home

SHORT TITLE:

with students living within walking distance of the school. We will try to target those living close to the school but it is likely that some students living further away will receive the flier.

We did not receive very many returned screeners. Thus, we are going to recruit more broadly as described above. We will screen those who respond to the recruitment flier to determine their eligibility. These eligibility questions were asked in the Phase 1 screener survey, but need to use the Phase 2 phone script as a screener because we won't have Phase 1 data on everyone who we send the recruitment flier to.

- 14.2 The participants will come from Banneker elementary school.*
- 14.3 Phase 1 will include all students at Banneker. Phase 2 will involve a select group of students selected based on their survey responses. A Letter of Support from the school is included in this IRB application.*
- 14.4 No identifiers will be collected prior to p/a/c by the CMH study team.*
- 14.5 For Phase 2, study staff will contact a select subset of survey respondents up to three times to offer the intervention, and share the flier with other families (including those who did not respond to the screener) until up to 30 dyads agree to receive the intervention. First, a recruitment letter will be sent in the mail and email. Next, we will call the parent on the phone and go over the details of the study and screening (if interested). At this time, the parent and child will either agree to participate or decline. The intervention will start the Sunday after enrollment.*

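### Does the forecast of 600 Phase 1 respondents need correcting now that Section 14.1 reports few returned screeners?

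*Combined protocol and SAP*

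**What the plan says.** The Study Summary (1.0) says the survey goes home with every enrolled student and that the "estimated response is 600 parents". Section 13.1 repeats it: "anticipated that 600 parents will respond to the survey". Phase 2 is set at up to 30 parent/child dyads.

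On coverage, Section 3.0 says the research activities "involve a cross-sectional survey of all students in the school (Phase 1"), and Section 14.3 says "Phase 1 will include all students at Banneker". Sections 1.0 and 14.1 are narrower and speak only of sending the form home.

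Section 14.1 then reports what happened: "We did not receive very many returned screeners". It goes on to say "These eligibility questions were asked in the Phase 1 screener survey", which identifies the screener as the Phase 1 survey. It adds that "we won't have Phase 1 data on everyone who we send the recruitment flier to". Section 14.5 describes the wider recruitment: staff will "share the flier with other families (including those who did not respond to the screener").

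Section 20.1 plans descriptive summaries of the surveys, and 20.2 gives a sample size rationale in terms of dyads who finish the intervention and the closing survey.

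**The concern.** A reader who stops at the summary or at 13.1 would put Phase 1 at about 600 parents. A reader who reaches 14.1 learns that returns were few. Both statements stand in the operative text, not in a list of past changes, so neither can be set aside as superseded. The amendment that brought in the flier route left the Phase 1 size and scope statements as they were.

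The wording of 3.0 and 14.3 adds to this. If Phase 1 is taken to cover the whole school, percentages on travel mode, barriers and interest in walking might be read as school-wide figures. They would in fact come from a self-selected group of unstated size. Families keen on walking may be more likely to return the form, although the documents do not establish that. At stake is how Phase 1 results are read in a report: their denominator, and how far non-response could distort them.

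**Working it through.** **Can the 600 be reproduced?** No. The documents give no enrolment, no number of surveys sent, no assumed response rate and no precision target. Working backwards, surveys needed = 600 / r for an assumed return rate r:

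| Assumed r | Surveys needed |
|---|---|
| 100% | 600 |
| 80% | 750 |
| 60% | 1000 |
| 50% | 1200 |
| 30% | 2000 |

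Nothing in the text selects a row, so the figure can be neither confirmed nor refuted.

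**Does anything depend on it?** Section 20.2 justifies the sample size by Phase 2 dyads. Section 20.1 plans no test. A smaller return would widen any interval around a percentage. For a share of 50%, the 95% half-width is 1.96 × √(0.25/n): 4.0 points at n = 600, 9.8 at an assumed n = 100 and 17.9 at an assumed n = 30. These values take simple random sampling and ignore non-response bias. The plan sets no precision target that they could miss.

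**Does the ratio to Phase 2 show the size of the shortfall?** 600 / 30 = 20 expected responses per place, so 30 / 600 = 5% of the forecast would fill Phase 2 if every respondent were usable. They are not all usable. Section 11.1 requires interest in walking, limits use of the before- and after-school programme, and requires suitable residence or willingness to use a remote drop-off. Section 14.1 adds purposeful selection, and 14.5 lets families decline. Failure to fill 30 places from the screeners therefore says little about how many came back.

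**How far could non-response distort a school-wide percentage?** If nothing is known about non-respondents and a share p is seen among a returned fraction r, the school-wide value lies between p·r and p·r + (1 − r). The width is 1 − r: 90 points at r = 10%, 75 at 25%, 50 at 50%. These rates are assumptions, and the bound concerns a quantity the plan does not set out to estimate. The Phase 1 objective in 2.0 is to find interested families.

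**Do the passages conflict?** An estimate made before the survey and a report made after it can both be true. For coverage, 1.0 and 14.1 define what was done with all students: the form was sent home. The respondents are parents (1.0, 11.1, 13.1), so a survey of all students can only name the group approached. Section 14.5 speaks openly of families who did not respond.

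**The case for a change.** The best argument for a change comes from Section 25.1. Under the opt-out process there, a family declines by not completing the form. By the protocol's own rule non-returners are not participants, so the statement in 14.3 that Phase 1 will include every student cannot be literally true. In a descriptive survey, the numbers distributed and returned are also the basic facts needed to interpret any percentage, and the plan gives neither. The remedy would be cheap: a few wording edits and two counts, although the number distributed might have to come from the school.

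Most of this stands as a description of the text. Section 14.3 is loosely worded, the 600 carries no note that events have overtaken it, and the return rate does belong beside the results. It does not show that following the plan would go wrong. Realised counts are results, and 13.1 is a field for planned numbers. Only returned forms can be summarised under 20.1, so the respondents are the denominator whether or not the section says so. The risk that someone reads the percentages as school-wide lies in a future report, since the plan makes no such claim.

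**Conclusion.** No change to the plan follows. The mismatch is an outdated forecast left beside a later and candid report of low returns, together with two phrases that are looser than the distribution statement in 1.0 and 14.1. The shortfall is unknown, because 14.1 gives no count. The effect on the planned analyses is nil, because no calculation, test or decision uses the 600 and the Phase 2 target of up to 30 dyads has its own rationale. The practical consequence of the low return, too few candidates for Phase 2, was already met by the flier route.

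This rests on two readings: that Phase 1 is a means of finding interested families, as 2.0 states, and that its percentages will be presented as describing respondents. A competent analyst would give the numbers distributed and returned with those percentages unprompted. If the results were instead offered as estimates for the whole school, non-response would become a substantive issue for that report.
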